6.1.2 Product Storage and Stability

The trial product and placebo will be stored in a dark, cool (4⁰C-40⁰C), dry place away from acids, alkaline materials, heat, and bleach. The containers will be stored in a locked, controlled, secure environment. Shelf life has been established by the manufacturer as 3 years. Access to the trial product and placebo will be limited to IRB-approved trial personnel only. Drug accountability ([Section 6.4](#)) will be closely monitored at each trial site.

6.2 Dosage, Preparation and Administration of Trial Product

Teeth that meet the inclusion criteria will be assigned to SDF application (treatment) or placebo (control), following the manufacturer's recommendations. No caries removal will be performed. Lesions will be cleaned with a toothbrush or microbrush to remove food debris and gross visible plaque, and dried with cotton/gauze, and the solution will be painted on the dentin of each targeted cavitated lesion using a standardized applicator. The amount used will be recorded as multiple ampules may be required to treat multiple carious lesions (up to 2 ampules-each containing approximately 100 μ L, will be used per child, per application visit).

Universal precautions will be followed to protect participants and clinicians from exposure to potentially infectious fluids and materials.

6.3 Modification of Trial Product Administration for a Participant

No modifications of trial product administration are anticipated as the lethal dose (LD50) of SDF subcutaneously ranges between 440 and 442 mg/kg. Each ampule contains a drop. One drop (approximately 100 μ L) is ample material to treat several teeth, but for a child with S-ECC, 2 drops may be needed depending on the number of teeth to be treated. One drop of Advantage ArrestTM (38.3% to 43.2% SDF) contains 38-43.2 mg SDF. Two drops would contain 76-86.4 mg SDF. Assuming children in this trial (1-5 years of age) weigh 10-18 kg (50th percentile based on the Centers for Disease Control and Prevention growth curves), for a 10 kg child, and an SDF dose for 2 drops (maximum amount used per child per application visit) of 76-86.4 mg, the dose would be 7.6-8.6 mg/kg. Thus, the relative safety margin of using 2 entire drops on a 10 kg child is: 440 mg/kg subcutaneous LD50 / 8.6 mg/kg dose = 51-fold safety margin. As this trial will apply SDF at 2 separate visits, the total possible dose during the trial is doubled compared to the previous calculations, and the safety margin is 25.5-fold.

6.4 Accountability Procedures for the Trial Product

Trial product and placebo will be shipped directly from the manufacturer to each of the 3 clinical trial sites. The product should be stored in a dark, cool (4⁰C-40⁰C), dry place away from acids, alkaline materials, heat, and bleach. There will be a manifest each time product is shipped, and a receipt/tracking record maintained at each clinical trial site.

[figure not shown]
Investigational product accountability logs, including stock records and participant records, are to be utilized at each trial site for trial product accountability. Detailed instructions for product accountability will be contained within the MOP.

6.5 Concomitant Medications/Treatments

The date of last FV treatment will be recorded at baseline, 1.5-, 3-, 4.5-, 6-, 7- and 8-month visits. FV will not be applied the same day as SDF; time between FV and SDF applications must be at least 12 hours.

Concomitant medications associated with any adverse events which occur will be recorded.

7 TRIAL SCHEDULE

	Screening/Baseline	24-48 Hour Contact	1.5 Month Contact	3 Month Visit	4.5 Month Contact	6 Month Visit	24-48 Hour Contact	7 Month Contact	8 Month Visit	Unscheduled Contact	Unscheduled Visit	Withdrawal Visit
Informed Consent	X											
Medical History	X				X	X						
Oral Soft Tissue Exam	X		X		X	X		X		X	X	X
ICDAS Exam	X				X	X			X			X
SDF/Placebo Application	X					X						
Photographs of Teeth	X		X		X	X		X		X	X	X
Oral Hygiene/Diet Education	X				X	X			X			X
DDQ (Pain)	X	X		X	X	X	X		X	X	X	X
OHRQoL	X				X	X				X		X
Family Survey	X	X			X		X			X		X
Adverse Events	X	X	X	X	X	X	X	X	X	X	X	X
FV History Check	X			X	X	X	X		X	X		X

7.1 Consenting Process

Prior to the collection of any trial data, consent will be obtained by trained trial personnel. Parents or legal guardians will review the consent document with trained trial personnel. Parents or legal guardians will be allowed time to review the consent document and all questions will be answered before the parent or legal guardian consents to participate. Additionally, parents and guardians will be instructed that participation in this or any research trial is totally voluntary and deciding not to participate will not affect their ability to receive other examinations or future treatment through oral health clinics. The parent/legal guardian will be informed that they are consenting for their participation in the trial, as well as that of their child. Consent will be documented using IRB-approved and stamped consent forms. The consent process will be documented on a source document which ensures the steps of the consenting procedure have been followed.

Consent forms will be translated by a translator into selected languages. In addition, trial personnel fluent in selected languages will be available at sites if needed.

7.2 Screening/Enrollment/Baseline

Prior to the initiation of any trial procedures, the Site Coordinator will confirm written informed consent has been obtained from the parent/legal guardian, and confirm that the adult/child pair meets the eligibility criteria (except for tooth inclusion, which requires the ICDAS exam to be completed).

The parent/guardian will be asked to complete a brief medical history for the child, and the trial questionnaires. This could occur on a day other than the ICDAS examination, but must occur after informed consent is obtained.

The child will be examined by a calibrated trial examiner, who will be masked to treatment allocation and responses on the trial questionnaires. The examiner will review the medical history and the inclusion/exclusion criteria. After doing a soft tissue exam, teeth will be cleaned with a toothbrush to remove food debris and gross plaque, and a full mouth exam will be done using a clinical examination headlight, mirror, and cotton/gauze. The ICDAS examination will be conducted scoring the teeth for lesion severity and hardness/activity (Appendix A). Randomization will occur after the baseline ICDAS exam is completed and it is verified the child has eligible trial teeth. The parent/guardian, child and trial examiners/team will remain masked regarding trial group allocation.

If the adult/child pair meets eligibility criteria, all teeth that meet the inclusion criteria will be targeted for treatment. Administration of the trial drug/placebo is detailed in [Section 6.2](#) of the protocol as well as the MOP. Photographs may be taken of the child's teeth/mouth but not including the face or other identifying features for illustration and publication purposes. Frankl score, a measurement of child behavior, will also be recorded. All children will receive advice on diet, brushing with a small amount of F toothpaste under supervision, and will receive a toothbrush and fluoride toothpaste. Parents will be advised not to use F toothpaste the evening after the application.

Trial drug/placebo application will not be performed the same day the child is receiving a FV application as part of usual care; time between FV and SDF applications must be at least 12 hours.

7.3 Intermediate Visits

7.3.1 24- to 48-Hour Safety Contacts (± 8 hours)

All participants will be contacted 24- to 48-hours after the baseline and 6-month trial visits to inquire if any Adverse Events (AEs), Serious Adverse Events (SAEs), or Unanticipated Problems (UPs) have occurred. This could be via a phone call, email, text, etc., or in person, if possible. All events will be recorded and reported, and the child will be brought in for an unscheduled visit as required. Additionally, the four questions from the Family Survey which refer to treatment acceptability may be asked at this time.

7.3.2 24- to 48-Hour Safety Visits (± 8 hours)

In addition to the 24- to 48-hour safety contacts, a safety visit 24- to 48-hours following application of the trial drug/placebo will be available for each participant after the baseline and 6-month trial visits. An intraoral soft tissue examination, including examination of the gingiva, will be performed. The status of the intraoral soft tissues will be recorded, and children with an AE (e.g., gingival irritation), SAE, or UP will be monitored until resolution of the problem or referred for treatment, if necessary. Refer to Appendix E and the MOP for additional details.

7.3.3 1.5-, 4.5-, 7-Month Intermediate Contacts (± 10 days)

Intermediate contacts will occur approximately 1.5, 4.5, and 7 months post baseline, and will allow the trial team to ask brief questions to inquire if any AEs, SAEs, or UPs have occurred, in addition to administering the tooth pain questionnaire to determine if an unscheduled trial visit is necessary to

evaluate the child. Additionally, medical conditions may be updated at the 4.5 month intermediate contact in order to confirm eligibility for the second application of SDF/placebo at the 6 month visit. These contacts will occur by a variety of strategies, including via phone, email, online survey, etc. The contacts will help to enhance retention.

All AEs, SAEs, and UPs will be recorded and reported. Trial teeth that cause pain due to caries, pulpal exposure, mobility, signs of pulpal infection (abscess, fistula, swelling) will be exited from the trial and referred for appropriate care (**early exit strategy**), and will be considered treatment failures in the analysis of the efficacy outcome.

7.3.4 Three-Month Visit (± 19 days)

Trial participants will be asked to attend a trial visit at the early childhood education program or a central location (may vary by trial site) approximately 3 months post-baseline. This visit will include: an intraoral soft tissue oral exam, a full-mouth ICDAS exam, including an assessment of color and hardness of all cavitated lesions (regardless of whether included or not in the trial), potential photographs of the child's teeth/mouth but not including the face or other identifying features for illustration purposes, assessment of AEs, SAEs, and UPs, recording Frankl behavior score, and trial questionnaire completion by the parent/legal guardian. If the parents/guardians are not in attendance, parents will be contacted via preferred contact method to obtain questionnaire responses. If a trial tooth meets the criteria for an "early exit strategy", it will be exited from the trial and referred to appropriate follow-up care. The tooth will be considered a treatment failure in the analysis of the primary endpoint. All children will receive written advice to take home on diet, brushing with a small amount of fluoridated toothpaste under supervision, and will receive a toothbrush and fluoridated toothpaste.

7.3.5 Six-Month Visit (± 19 days)

Trial participants will attend a trial visit at the early childhood education program or a central location (may vary by trial site) approximately 6 months post-baseline. This visit will be identical to the 3-Month Visit described in 7.4.4, but in addition, medical history will be either re-assessed or reviewed from the 4.5 month contact to confirm eligibility and then the SDF/placebo will be re-applied to all cavitated trial lesions. Data from the 6-month visit will be used to assess the primary outcome of the trial.

7.4 Final Trial Visit: 8 Months (± 19 days)

Trial participants will be asked to attend a final trial visit at the early childhood education program or a central location (may vary by trial site) approximately 8 months post-baseline. This visit will be identical to the 3-Month Visit described in 7.3.4. Additionally, final assessment of the treated teeth will be provided to the family. Follow-up care referrals will be facilitated by the trial team.

7.5 Withdrawal Visit

A withdrawal visit will occur for participants who withdraw or are withdrawn from the trial. The withdrawal visit will mirror the 8-month trial visit. If a participant cannot or will not attend the withdrawal visit, this information will be recorded.

7.6 Unscheduled Visit

In the event there are signs (abscess, fistula, and swelling) or symptoms (pain) of infection at any point, an unscheduled visit will be offered to the parent/legal guardian and child by the trial team. A clinically-warranted examination will be conducted, an assessment for AEs will be performed, and the participant will be referred for treatment if necessary. AEs will be reported per IRB guidelines.

7.7 Unscheduled Contact

Parents/legal guardians of trial children will be instructed to contact the trial team if they have any concerns at any point in the trial (e.g., believe their child is in pain). When the parent contacts the trial team, an assessment for AEs will be performed, the DDQ will be collected, and the participant will be scheduled for an unscheduled visit as necessary. AEs will be reported per IRB guidelines.

8 TRIAL PROCEDURES / EVALUATIONS

8.1 Trial Procedures/Evaluations

8.1.1 Clinical Examination

A clinical assessment will be conducted with each child participant. This will consist of the following.

- Teeth: A full mouth ICDAS examination will be conducted, and lesion hardness will be assessed using the ICDAS II system activity criteria for lesions with score ICDAS 5-6. See Appendix A.
- Intraoral soft tissues: The intraoral soft tissues will be examined for pathology and signs of infection. For details refer to the MOP. The clinical criteria for odontogenic infection are the presence of swelling, dental abscess, or a draining sinus in the tissue closely surrounding the tooth. Assessments for odontogenic infection or other intraoral infections are made at each clinical trial visit and unscheduled/emergency visit. Assessment of mucosal irritancy will be made by the trial examiner or hygienist, using a modification of an oral mucositis scale developed for radiation-induced mucositis (Sonis et al., 1999).

8.1.2 Questionnaires

- Medical history will be assessed at baseline and reviewed at approximately 6 months or between 4.5 and 6 months.
- Assessments for tooth pain are to be made at each trial visit throughout the child's participation in the trial using the Dental Discomfort Questionnaire (DDQ) (Appendix B; Versloot et al., 2006), to be completed by the parent/guardian. More details are provided next: Given that pain is a subjective experience, pain in general is most reliably measured using self-report (FACES pain scale and Wong-Baker FACES scale) in children (Hicks et al., 2001; Baretto et al., 2004; Versloot et al., 2004). Assessing pain in preschoolers presents special challenges, as their cognitive capacities are still under-developed making it difficult for them to communicate verbally, and consequently reliably self-report pain. To avoid inaccurate assessment of pain in very young children, it is recommended to use a validated observational tool that assesses pain as reported by parents/legal guardians as proxies based on the observation of pain-related behaviors by the child. The DDQ (Appendix B; Versloot et al., 2006), a behavioral observation tool developed and validated to recognize toothache in children aged 5 or younger, focuses on toothache-related pain behaviors.

This validated questionnaire consists of two parts. The first part includes a question concerning the occurrence of toothache. This question can be answered with: 'never', 'sometimes', 'often' or 'I do not know'. If the parent answers 'sometimes' or 'often', they are asked when. Choices include: either during meals, during daytime or nighttime (several alternatives possible). The second part of the DDQ consists of 8 validated questions about different behaviors associated with toothache or discomfort due to caries (e.g., crying during meals or chewing problems). For each item the parent is asked to rate how often their child shows a given specific behavior. The questions can be answered on a three-point scale: 0 'never', 1 'sometimes', and 2 'often'. According to Versloot et al. (2006), 70% of children with cavities and toothache had a DDQ score of 4 or higher, and the average score for these children was 5.73. However, for ethical reasons in this study, any complaint of toothache pain (DDQ score of 1 or higher) will result in the study team attempting an unscheduled visit to examine the child to assess whether the tooth still meets eligibility criteria for the trial or needs referral for care.

Assessments for presence of pain and level of pain (score of the DDQ) will be made at each trial visit, intermediate contact, and unscheduled/emergency visit in the trial using the DDQ. The total number of pain episodes associated with trial teeth per child will be assessed.

- Systemic effects/allergic reaction will be assessed at each trial visit and interim trial contact, either by examiner observation or by soliciting information from parents about the following adverse events: nausea, not eating, vomiting, difficulty swallowing or breathing, swelling around the lips or skin of the face, itchiness around the lips or skin of the face, hives or rash, stomach ache, or diarrhea.
- OHRQoL will be measured at the baseline, 3-, 6-, and 8-month trial visits throughout participation in the trial. Parents/guardians will be asked to complete a 16-item Parental-Caregiver Perception Questionnaire (P-CPQ) and an 8-item Family Impact Scale (FIS) questionnaire (Thomson et al., 2013; Appendix C). The rationale is that for children under six years of age, the use of simple child-completed scales, or questionnaires completed by parents/legal guardians as proxies, is the usual approach. Parents/legal guardians will be asked to complete the 16-item P-CPQ and 8-item FIS questionnaire. These measures have been found to be reliable, valid and responsive in children with severe-ECC, and help measure different aspects of the oral health condition. The P-CPQ estimates the nature and magnitude of the effects of the condition on the child's OHRQoL, considering not just pain, but the impact on their overall well-being (e.g., how they eat, play with others/socialize, look/teeth appearance, etc.). The FIS enables determination of the impact of the child's condition on the family. These scores will be compared at each trial visit against an accepted single-item (global) self-rating or overall well-being question, which serves as a summary measure of the same construct. In addition, a global transition judgment question will be included at follow-up visits for assessing the responsiveness of these measures to SDF treatment in children with ECC (Locker et al., 2004). For details see Appendix C.
- The Family Survey (Appendix D) including questions about treatment acceptability and satisfaction will be completed at baseline/24-48 hour contacts/visits, and 3-, 6-, and 8-month trial visits. Satisfaction with treatment will be assessed using a well-validated tool (the Post-Surgical Patient Satisfaction Questionnaire; Kiyak et al., 1984); and in addition, the Client Satisfaction Questionnaire (which is an 8-item, easily administered and scored instrument designed to assess client satisfaction with services) which has been adapted for this project (Larsen et al., 1979; Attkisson and Zwick, 1982). A question will be asked after the placement of SDF/placebo regarding the acceptability of the treatment (i.e., was the treatment tolerated by the child), as there is evidence that different types of treatment may influence children's behavior and perceptions of their dental treatment (Santamaria et al., 2015).

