In four randomized clinical trials in which multiple teeth were treated with SDF for dental caries in preschool children, school-age children, and elders, not a single unexpected adverse event was reported (Llodra et al. 2005; Chu et al., 2002; Tan et al., 2010; Liu et al., 2012). In the Llodra et al. study (2005), 3 out of 225 children treated with SDF had transient mildly painful white lesions on the gingival surface near the tooth treated. These lesions resolved without treatment in 48 hours when the children were re-examined. These transient effects, although mildly adverse, were not unexpected. In a recent study in the US, targeting 3-5 year old children in Head Start centers, 38% SDF or placebo was applied (Milgrom et al., 2018). Within 24 to 48 hours of treatment, trained staff contacted parent/caregivers by telephone about adverse events. The questions included: (1) Has your child required medical care since his/her dental visit in the last 48 hours? (2) Has your child been to an emergency room, medical doctor, nurse or health care provider? (3) Since receiving the solution on the teeth has your child experienced any of the following? Nausea, not eating, vomiting, difficulty swallowing or breathing, swelling around the lips or skin of the face, itchiness around the lips or skin of the face, hives or rash, stomach ache, or diarrhea. Eight adverse events were reported by parents, 4 in each group. Based on enrolled participants, the adverse event rate was 11.1% in the placebo group (exact 95% CI: 3.2 to 26.7%) and 13.3% in the 38% SDF group (exact 95% CI: 3.7 to 30.7%). Based on all contacted participants, the adverse event rate was 15.4% in the placebo group (exact 95% CI: 4.3 to 34.9%) and 16.0% in the 38% SDF group (exact 95% CI: 4.5 to 36.1%). There were no statistically significant differences by treatment. The type of adverse event, severity and relationship of the adverse event to the treatment condition are reported in the Tables 1 and 2 below. The majority of the adverse events were either diarrhea or stomach ache, mild in severity and all resolved within 2 days of reporting. At the follow-up visit 14 to 21 days after treatment, a dental provider performed a visual examination to detect gingival or soft tissue stomatitis or ulcerative lesions. No participant was identified at that point with gingival or soft tissue stomatitis or ulcerative lesions.

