2.3 Potential Risks and Benefits

2.3.1 Potential Risks

Potential SDF-affiliated risks to human subjects include: discoloration of cavitated lesions, possibility that treated lesions will progress between enrollment and the 8-month final trial visit if the SDF does not arrest the lesion, transient metallic or bitter taste, and temporary irritation of soft tissues (e.g., erythema, ulceration) after application. Similar risks apply to the placebo group, as lesions may discolor and progress between enrollment and the 8-month final trial visit. If SDF contacts the skin there may be a temporary tattoo that will resolve within 2 weeks. Potential safety risks associated with an allergic reaction or gastrointestinal disturbances will be assessed during the trial, to include: nausea, not eating, vomiting, difficulty swallowing or breathing, swelling around the lips or skin of the face, itchiness around the lips or skin of the face, hives or rash, stomach ache, or diarrhea. Other risks associated with trial procedures include potential trauma as a result of the ICDAS examination, (this risk is no greater than the risk from a traditional dental examination); cross-contamination associated with the ICDAS and intraoral photographs; and potential loss of confidentiality. Additionally, the trial questionnaires pose minimal risk of discomfort as they do not contain any disturbing material.

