Diarrhea	Increase of <4 stools per day over baseline; mild increase in ostomy output compared to baseline	Increase of 4 - 6 stools per day over baseline; moderate increase in ostomy output compared to baseline	Increase of >=7 stools per day over baseline; incontinence; hospitalization indicated; severe increase in ostomy output compared to baseline; limiting self-care ADL
Nausea	Loss of appetite without alteration in eating habits	Oral intake decreased without significant weight loss, dehydration or malnutrition	Inadequate oral caloric or fluid intake; tube feeding, TPN, or hospitalization indicated
Extraoral (mucosal) Staining	Staining on skin	-	-
Intraoral (mucosal) Staining	Staining on mucosa	-	-

Based on AE reports for SDF from the literature. Developed from Common Terminology Criteria for Adverse Events, version 4.03, US Department of Health and Human Services, 2010.

Any related AE graded severe will be immediately reported to the Medical Monitor and investigated.

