6.12.1. Adverse Events

All reported AEs will be coded using the Medical Dictionary for Regulatory Activities (MedDRA) and summarized by System Organ Class (SOC) and Preferred Term (PT).

Analyses of AEs will be performed for those events that are considered treatment emergent AEs (TEAE), where treatment emergent is defined as: any AE with onset after the administration of study drug (SDF or placebo).

An overall summary of AEs without SOC and PT will be presented with the number and percentage of participants by treatment with any of the following types of AEs:

- TEAE
- TEAE by severity (mild, moderate, severe, life-threatening, fatal)

- TEAE by relationship to study drug (unrelated, related; where unrelated includes not related and unlikely related, and related includes possibly related, probably related, related)
- Serious TEAE
- TEAE leading to study drug discontinuation
- TEAE leading to death

In addition to the overall summary, the number and percentage of participants by treatment for each of the TEAE categories above will be summarized by SOC and PT. In these summaries, each participant will contribute only once to the incidence rate based on the most related occurrence and most severe occurrence of the AE. This is true regardless of the number of occurrences.

Summaries of TEAEs by SOC and PT will also include total number of unique AE occurrences, where unique AE occurrences include all events, regardless of whether the same participant experiences the same AE multiple times. However, if the end of a first occurrence and the start of a subsequent occurrence overlap, or the end of a first occurrence indicates “ongoing”, then this would be counted as only one occurrence.

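### The symptoms solicited from parents omit the local harms the protocol names, the timely mouth exam is offered rather than required, and the SAP divides by all treated children, so local-event rates are likely to be understated

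*Protocol*

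**What the plan says.** Protocol 2.3.1 lists among the product's risks "transient metallic or bitter taste, and temporary irritation of soft tissues (e.g., erythema, ulceration) after application" and adds: "If SDF contacts the skin there may be a temporary tattoo that will resolve within 2 weeks".

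The only list that the protocol says is put to parents is in 8.1.2: "soliciting information from parents about the following adverse events: nausea, not eating, vomiting, difficulty swallowing or breathing", then facial swelling, itching, hives or rash, stomach ache and diarrhea. The same symptoms recur in 9.1. Section 9.1 also says that gingival irritation is recorded, but gives no parent question for it.

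For the period just after application, 7.3.1 has every family contacted with a general question about adverse events. Section 7.3.2 adds that "a safety visit 24- to 48-hours following application of the trial drug/placebo will be available for each participant", and Section 4 describes the visit in the same optional terms. The visit is specified as an intraoral soft-tissue exam. Section 16.3, which covers the baseline and 24-48 hour contacts or visits together with the main visits, says that a soft-tissue exam is done, without calling it optional.

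In SAP 6.12.1, "the number and percentage of participants by treatment for each of the TEAE categories above will be summarized by SOC and PT". The population is the Safety Population, which SAP 6.2.3 defines by treatment received and not by whether the child was contacted or examined.

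**The concern.** A short-lived local effect can enter the database in three ways: a specific question, a general question, or an examiner looking in time. For the local harms in 2.3.1 the protocol specifies no specific question, and the timely look is optional. A child who is not examined and whose parent volunteers nothing is counted as event-free in a percentage taken over all treated children.

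The result pulls local-event rates downward. SAP Section 9 removes formal testing of adverse events, so these descriptive percentages are the safety result, and the same section refers to a pre-NDA meeting. The protocol's precision statement for the 24-48 hour visit (12.2) is also worked out for the study sample, which amounts to assuming that nearly every child is examined.

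**Working it through.** **1. Which route covers which harm**

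| Harm named in 2.3.1 | On the 8.1.2 list | Within the 24-48 h intraoral exam | Row in Appendix E |
|---|---|---|---|
| Soft-tissue irritation | No | Yes | Yes (oral mucositis) |
| Metallic or bitter taste | No | Not specified | No |
| Skin staining | No | Not specified | Yes ("Extraoral (mucosal) Staining") |

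For taste and skin stain, attending the optional exam does not by itself close the gap.

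**2. Timing**

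- Painful white gingival lesions in a cited trial (3 of 225 children, Protocol 2.2): "These lesions resolved without treatment in 48 hours when the children were re-examined".
- Higher erythema scores at one site of the adult study in 2.2: present at 24 hours, no difference from placebo at seven days.
- Skin stain: gone within 2 weeks (2.3.1).
- Next scheduled exam after the first application: day 71 to 110 (SAP 6.4.1).

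The 3-month exam therefore comes too late for all of these.

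**3. The plan's own precision figure**

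Inputs from 12.2 and 5.4: event rate p = 15%, no true difference, 1144 children allocated 1:1, so n = 572 per arm. The stated result is an upper bound no more than 4 points above the observed difference.

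Distance to the bound = z × √(2p(1−p)/n)

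- One-sided 95%, n = 572: 1.645 × √(2 × 0.15 × 0.85 / 572) = 3.47 points.
- One-sided, n = 515 (10% attrition): 3.66 points.
- Two-sided, z = 1.96, n = 572: 4.14 points, which agrees only after rounding.

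The figure reproduces as a one-sided bound if nearly everyone is examined. Solving for 4 points: n = 2 × 0.15 × 0.85 × (1.645/0.04)² ≈ 431.2, so 432 per arm, and 432/572 = 75.5%.

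**4. Effect of attendance and of the general question**

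Let a be the share attending the exam and s the share of events in unexamined children that the general question captures. The documents give neither; both are assumptions.

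Recorded rate = true rate × [a + (1−a)s]

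For example, at a = 60%: 15% × 0.60 = 9% with s = 0, and 15% × (0.60 + 0.40 × 0.5) = 12% with s = 0.5.

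| Attendance a | Recorded rate for a true 15%, s = 0 | s = 0.5 | One-sided bound among examined, n = 572a |
|---|---|---|---|
| 100% | 15% | 15% | 3.47 points |
| 75% | 11.3% | 13.1% | 4.01 |
| 60% | 9% | 12% | 4.48 |
| 50% | 7.5% | 11.3% | 4.91 |
| 25% | 3.8% | 9.4% | 6.95 |

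If a and s are equal in both arms, a true difference shrinks by the same factor. An illustrative 5 points becomes 5 × 0.6 = 3 to 5 × 0.8 = 4 points at 60% attendance, and 2.5 to 3.75 at 50%.

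The 15% is the planning value in 12.2. It combines erythema with general adverse-event rates, so it illustrates the proportion lost and is not an estimate of the local-event rate.

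**The case against.** **Parents are asked.** Every family is contacted at 24 to 48 hours and asked about adverse events (7.3.1), spontaneous reports count (9.1), and parents are told to call with concerns (2.3.1, 7.7). A skin stain is easy for a parent to see. The item on not eating, and the Dental Discomfort Questionnaire where given, may pick up some mouth irritation. This stands. A reader might infer that unexamined children have no way to report a local effect, or that each is bound to be counted as event-free; the documents do not support that. What remains is that an open question may capture less than a specific one.

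**The list may not be the script.** It appears under systemic effects and allergic reaction, and mucosal irritation is assigned to the examiner (8.1.1, 9.1). The Manual of Procedures, not available here, may hold fuller questions. This stands as a caveat on the missing prompts; it does not touch the denominator.

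**The exam may be for everyone.** Section 16.3 can be read so, 12.2 sizes the visit on the study sample, and 5.3.1 pays for each safety visit. Against this, Section 4 and 7.3.2 both make it optional. The conflict is real, and if all children attend, understatement of what an intraoral exam can detect disappears.

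**All treated children is a conventional denominator.** True, and it should stay. But the protocol reports an earlier Head Start trial on two denominators: 11.1% and 13.3% of enrolled placebo and SDF children, and then: "Based on all contacted participants, the adverse event rate was 15.4% in the placebo group", with 16.0% on SDF. The second denominator is thus already familiar to the authors.

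**It is late.** The SAP mentions a pre-NDA meeting and describes pandemic-era visits in the past tense. New prompts cannot recover past contacts. This stands, and is why the reporting change comes first.

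**Conclusion.** The point holds as a likely understatement of local-event rates. The missing prompts, the optional exam, the late next exam and the all-treated denominator are all in the text. The size is not. With half of the children examined, a true 15% would be recorded as 7.5 to 11.3% if the general question captures 0 to 50% of events in the rest. There is no understatement if attendance or capture is complete. The 12.2 precision is met with about three quarters of children examined and missed below that.

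Two stronger readings should be resisted. A reader might infer from the cited Head Start trial that unequal follow-up would create a false difference between arms. That trial's figures concern telephone contact in about 66 children, not attendance at an exam, and nothing in the documents shows that attendance differs by arm. A reader might also infer that these are the most frequent harms to expect. The protocol gives no frequency for taste or staining, and in the Head Start trial most events were diarrhea or stomach ache, which are on the list.

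**What to change.** 1. In SAP 6.12.1, for local events (mucosal irritation, staining, taste), report by arm and by application the number contacted, the number examined, and the event rate among those contacted or examined, beside the Safety Population rate. Restate the precision in Protocol 12.2 for the number actually examined.
2. Reconcile Protocol 7.3.2 (and Section 4) with 16.3 on whether the 24-48 hour exam is for every child.
3. For any contacts still to come, add questions on sore, red or white areas of gum or mouth, bad or metallic taste, and stain on skin or mouth, unless the script in the Manual of Procedures already has them. If it does, say so in the protocol.

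The cost is one extra table and, where contacts remain, a few questions on an existing form. Reported rates will be slightly higher. Asking about taste and stain carries a small risk to masking, which can be limited by keeping these answers from the caries examiner. If data collection is finished, items 1 and 2 remain useful on their own.
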